- Participation in another clinical trial of experimental treatment (does not include studies e.g. randomising patients to one of more stent types for PCI and following patients registry-based). Patients included in the national trial of hydralazine and metformin for heart failure may also be included
- Contraindication for establishing implantable device treatment
- Previously implanted CRT system
- Does not wish to participate

Endpoints:

Primary:

- Death or non-planned hospitalisation for heart failure
 - Death
 - Non-planned hospitalisation for heart failure (non-planned hospitalisation >24 hours due to heart failure requiring intensified heart failure therapy)

Secondary:

- Sudden death
- Cardiac death
- Clinical response defined as "*increase in NYHA class (≥ 1 class from baseline) or improved walking distance by 6MWT ($\geq 10\%$ from baseline)*" after 6 and 24 months
- 6MWT, changes from baseline to follow-up after 6 and 24 months
- NYHA class, changes from baseline to follow-up after 6, and 24 months
- Quality of Life (QoL) and patient reported outcomes (PROs), changes from baseline to follow-up after 6, 12, 24 and 48 months
- Echocardiographic endpoints (re-modelling of LV: LVESV, LVEDV, LVEF). See supplementary protocol on imaging
- ICD therapy (time to first and number of appropriate and inappropriate ICD therapy, respectively, in addition as ATP and shock therapy, respectively)
- Time to first episode of VT/VF
- Persistent atrial fibrillation
- Recently diagnosed atrial fibrillation (>30 seconds recorded by the implanted device)
- Procedure time at implantation, fluoroscopy time and dose
- Number of LV leads used at implantation
- Device-related complications (periprocedural: lead re-operation, pneumothorax, hemothorax, pericardial bleeding/tamponade and later (30 days post implantation): LV lead re-operation, device replacement due to battery depletion, and infection requiring extraction)
- Battery longevity (measured by ¹number of device replacements during the study period due to battery depletion and ² device battery longevity + estimated remaining device battery longevity as reported by the device at last study follow-up)

Study design:

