Post implantation, prior to discharge, and in the set device mode (DDD or VVI) ECG-12 with CRT, ECG-12 with pure RV pacing, and ECG-12 with pure LV pacing are recorded. At each follow-up ECG-12 is recorded when the patient arrives, with the existing device settings. The interval from RV pacing to activating the LV lead is measured at each follow-up visit. ECG's are recorded and stored digitally.

At each visit, the patient's current medication is recorded.

Patient-reported outcomes (PRO's):

At baseline and again after 6, 12, 24 and 48 months the following questionnaires will be used:

Kansas City Cardiomyopathy Questionnaire (KCCQ-12), 12 items

Patient Health Questionnaire (PHQ-9), 9 items

Generalized Anxiety Disorder (GAD-7), 7 items

At baseline in addition:

Expectations towards ICD therapy (EXPECT-ICD), 10 items

Brief Illness Perception Questionnaire (BIPQ), 9 items

Resulting in 47 items at baseline and 28 items after 6, 12, 24 and 48 months.

Details regarding PRO's shown in the PRO-appendix.

All patients are followed until the last included patient has been followed for at least 2 years.

If, at 3 months after implantation, there is no clinical response (defined as "*no improvement in NYHA class and <10% improvement of the 6MWT walking distance*") AV and VV optimisation guided by echocardiography is done in both groups. A separate protocol will be prepared for this optimisation.

In patients, who develop or have persistent atrial fibrillation, where sinus rhythm is not immediately obtained by medication and/or by DC cardioversion, there is a risk of a large frequency of intrinsic conducted ventricular activations without effective CRT. If effective CRT drops to <95% the patients are offered ablation of the AV node (His-ablation) or pulmonary vein isolation at the follow-up physician's discretion for the purpose of re-establishing effective CRT close to 100% of the time. If patients develop frequent ventricular extrasystoles that compromise effective CRT (to <95%), ablation for ventricular extrasystoles or medical antiarrhythmic treatment is offered at the follow-up physician's discretion. Atrial fibrillation and ventricular extrasystoles are handled equally in the two treatment arms.

Sample size:

Power calculation:

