- with QLV (time from QRS start to local LV activation where the LV lead is positioned) above/below the median value, respectively
- in NYHA class II and III/outpatient IV, respectively, at baseline
- with baseline LVEF above/below the median value, respectively
- with ischaemic and non-ischaemic background for heart failure, respectively
- with LBBB and non-LBBB, respectively
- with upgrade from RV pacing to CRT and primary implantation of CRT, respectively
- with the RV lead in a septal and non-septal position, respectively (RV lead position determined by flash CT after implantation)

- with the RV lead in an apical and non-apical position, respectively (RV lead position determined by flash CT after implantation)
- with and without echocardiography detected dyssynchrony, respectively (radial time-to-peak, cross-correlation and pattern-analysis) of LV
- scar tissue/perfusion evaluation by CT scan. Total percentage of scar tissue (higher/lower than median) as well as impact of scar tissue localisation with regard to the site of LV lead position (LV lead close to scar (in or in neighbour-segment in a 17-segment model of LV) or remote to scar.

Analysis for statistical interaction is done with respect to the subgroup-analysis above and presented graphically in a Forest plot.

Secondary endpoints are compared in a similar way using Cox regression or multipel linear or logistical regression analysis. In datasets with repeated measures, ANOVA is used. Whether data are normally distributed or not and whether single or repeated data determinations exist are taken into consideration. If relevant, competing risk is adjusted for in the analyses.

A p-value <0.05 is considered significant in two-sided test.

Adjudication of endpoints:

Monthly during the study/follow-up, the study secretariat will verify vital status for all included patients through the Civil Registration System (CPR). In case of death, the centre following the patient will gather information on the death from the patient's GP and from other hospitals/departments, if relevant. This information will be forwarded to the study secretariat coordinating the adjudication of endpoints. A copy of the death certificate is obtained, unless the cause of death is known (e.g. during hospital admission).

The endpoint committee consists of the members of the steering committee.

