Statisticians (Aalborg University Hospital)	[name]	([contact])
	[name]	([contact])
Analysis of Patient-reported outcomes (PRO's) (OUH)		
	[name], professor	([contact])

Responsible for imaging core-lab (RH)

[name]

[name]

[name]

[name]

Safety Committee

[name], Professor

[name]

[name]

Is the DANISH-CRT study feasible?

At present 950 CRT P/D implantations per year are performed in Denmark. It is estimated that at least half of these are eligible for a study as described here. Thus, we should be able to include 1000 patients within a maximum of 3½-4 years. At Aarhus University Hospital, mapping of the CS branches at CRT implantation is currently being investigated in a pilot study and provided the willingness to spend additional time on the implantations such a study set-up is feasible. Echocardiography and CT may be done in a clinical context in the departments.

We aim at financing a research nurse 20 hours/week at each CRT centre throughout the 6-year study period.

Information, inclusion and follow-up may be performed primarily by research nurses. Echocardiography will be performed by technicians/doctors. No need for PhD students for inclusion and coordination of pre-implantation imaging and analysis.

Aarhus University Hospital holds an internet-based CRF that can easily be extended and used for this study.

Is the study interesting?

The study will answer the question, whether mapping of LV activation in CS and positioning of the LV lead according to the latest local electrical activation is beneficial for the patient. Based on small studies in the literature, some physicians already search for late activation when implanting CRT systems, but the effect of this strategy has not yet been tested in a randomised controlled trial. The endpoint is clinically relevant and has been previously defined in correlation with heart failure and CRT. Dimensioning of the study is realistic.

The study can be conducted in a national collaboration. Recently, the study group completed the DANISH study in a national collaboration (15). In Denmark, CRT treatment is centralised to few high-volume centres, relatively high-volume physicians, and with a well-organised follow-up, feasible to complete including home monitoring in 95% of the enrolled CRT patients. Something that is quite extraordinary in an international perspective.

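### ANOVA is the only method named for repeated measures and no rule covers missing visits; read conventionally, it discards usable questionnaire data from patients who cannot reach month 48

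*Combined protocol and SAP*

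**What the plan says.** All places are in the combined protocol and SAP unless stated otherwise.

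- **Method (Data analysis).** "Secondary endpoints are compared in a similar way using Cox regression or multipel linear or logistical regression analysis". For longitudinal data: "In datasets with repeated measures, ANOVA is used". The next sentence adds: "Whether data are normally distributed or not and whether single or repeated data determinations exist are taken into consideration". Competing risk is to be handled where relevant. Nothing is said about missed visits, patients who die before a visit, or patients whose visit falls after closure.
- **PRO schedule (Endpoints, Secondary).** "Quality of Life (QoL) and patient reported outcomes (PROs), changes from baseline to follow-up after 6, 12, 24 and 48 months". The Protocol document's amendment entry of 11-01-2018 drops the 12-month questionnaires, which leaves 6, 24 and 48 months.
- **Walk test, NYHA class and echocardiography.** For the walk test: "6MWT, changes from baseline to follow-up after 6 and 24 months". The Follow-up section gives the same two time points for echocardiography and NYHA class.
- **Timeline.** Feasibility section: "Thus, we should be able to include 1000 patients within a maximum of 3½-4 years". Follow-up section: "All patients are followed until the last included patient has been followed for at least 2 years". Version 1 describes a 6-year study. The amendment entry of 19-01-2023 extends the study period to 31-12-2026.

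The plan also refers to a PRO appendix and a supplementary imaging protocol. Neither is among the documents reviewed, so a missing-data rule could stand there.

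**The concern.** In its conventional form, repeated-measures ANOVA needs a complete row of visits for each patient. A patient with good 6- and 24-month questionnaires but no 48-month one contributes nothing. Because follow-up may close 2 years after the last inclusion, many late recruits will lack month 48 for reasons of calendar date alone. Their earlier PRO data would be thrown away.

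Death and non-attendance are a different problem and affect every longitudinal endpoint. The trial's hypothesis is that the intervention lowers death or heart failure hospitalisation. If it does, patients with complete rows are selected by something that treatment influences, and the arm comparison among them is no longer protected by randomisation.

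These endpoints are also defined as changes from baseline, and the plan does not state that the baseline value will be a covariate. That gives away precision at no benefit.

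**Working it through.** The plan gives no figure for the share of patients reaching month 48, so there is none to reproduce. The event rates used below are those of its power calculation. They return its expected number of events: 432 × (0.35 + 0.26) = 263.5, stated as 264.

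**1. Share reaching month 48 by date.** With uniform accrual over A years and closure at T years after the first inclusion, the share is (T − 4)/A.

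| Scenario | A | T | Share |
|---|---|---|---|
| Closure 2 years after last inclusion | 3.5 | 5.5 | 1.5/3.5 = 43% |
| Closure 2 years after last inclusion | 4 | 6 | 2/4 = 50% |
| Full 6-year study | 3.5 | 6 | 2/3.5 = 57% |
| Extension, 6.5-year accrual (assumption) | 6.5 | 8.5 | 4.5/6.5 = 69% |

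The result depends on the shape of accrual. With closure 2 years after last inclusion, accrual falling linearly to zero gives 67% (A = 3.5) to 75% (A = 4); accrual rising linearly from zero gives 18% to 25%. Under the extension, a start between late 2017 and early 2018 and a last inclusion between end 2023 and end 2024 (dates not in the documents) would give about 70-84%.

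**2. Month 24.** The share is (T − 2)/A, which is 1 whenever T = A + 2. Every patient can reach it by date.

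**3. Adding deaths.** The plan expects half of the primary endpoints to be deaths. Applied to both arms, that is 0.35/2 = 17.5% and 0.26/2 = 13% by 4 years, a mean of 15.25%, so 84.75% are alive. Deaths after a first heart failure hospitalisation are not counted, so true survival would be lower.

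- Complete through month 48: 0.429 × 0.8475 = 36%; 0.50 × 0.8475 = 42%; 0.571 × 0.8475 = 48%; 0.692 × 0.8475 = 59%.
- With the plan's 10% withdrawal (× 0.9): about 327, 381, 436 and 528 of 1000, before any non-response.
- Alive at month 24, assuming a constant hazard: √0.8475 = 92%.

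**4. Cost in precision at month 24.** Using only patients complete to month 48, rather than all alive at month 24, widens a simple 24-month arm difference by √(0.921/0.363) = 1.59, √(0.921/0.424) = 1.47, √(0.921/0.484) = 1.38 or √(0.921/0.587) = 1.25. Withdrawal is taken as equal in both sets.

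**5. Scope for bias.** If the 25% reduction applied equally to deaths, 4-year mortality would differ by 17.5 − 13 = 4.5 percentage points between arms. The plan states that the study is not designed to show a mortality effect, so this is an illustration.

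**6. Baseline adjustment.** With equal variances and baseline-to-follow-up correlation ρ, the variance of the adjusted comparison relative to the change score is (1 − ρ²)/[2(1 − ρ)] = (1 + ρ)/2. At ρ = 0.5 this is 0.75 and at ρ = 0.7 it is 0.85, a reduction of 25% to 15%. The correlations are assumptions.

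**The case against.** The strongest reply is that the plan nowhere prescribes complete-case analysis. ANOVA can be fitted as a mixed model that keeps partial data, the same paragraph allows linear regression, and a change at a single visit can be regressed without dropping patients who lack a later one. This stands: listwise deletion is the conventional reading, not stated text. But the sentence on distribution and data structure does not mention missing visits, so the choice is left open until the data are in hand.

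Three stronger readings are tempting, and the documents do not support them.

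- *That all longitudinal results would come from early recruits.* Only the PROs have a 48-month visit.
- *That no more than half of the patients can reach month 48.* That needs uniform accrual and closure at exactly 2 years. The plan says at least 2 years, describes a 6-year study and was later extended.
- *That the missing 48-month visits themselves bias the comparison.* A late recruit lacks the visit because of enrolment date, and block randomisation within centre keeps enrolment dates similar across arms. That missingness mainly costs precision; bias would come from death and non-attendance.

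It is also fair that only secondary endpoints are involved. The primary time-to-event analysis is untouched.

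**Conclusion.** The concern holds in limited form. The repeated-measures method is under-specified, and its conventional reading is inferior to a readily available alternative. For the PROs, 31-57% of patients would lack month 48 by date alone across the tabulated scenarios. A conventional ANOVA over all visits would also lose their earlier questionnaires, making 24-month intervals about 1.25 to 1.6 times as wide. These sizes rest on uniform accrual, the assumed closure dates, the plan's death share and a constant hazard. For the walk test and echocardiography there is no loss by date. What remains is loss from death, withdrawal and non-attendance, with possible bias if the intervention affects survival or attendance; the documents do not allow its size to be stated. The conclusion would soften if the PRO appendix or imaging protocol already contains a missing-data rule.

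**What to change.** In the Data analysis section, replace ANOVA for continuous repeated endpoints with a likelihood-based linear mixed model using all available visits. Include baseline value, randomisation stratum, centre, visit, arm and arm-by-visit, with an unstructured covariance. State that patients not yet at month 48 at closure contribute their earlier visits.

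The model assumes that data are missing at random and does not by itself say how death counts. Add one sensitivity analysis that incorporates death, for example by ranking it as the worst outcome.

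Naming month 24 as the main PRO contrast, with month 48 supportive, is optional; the plan sets no order among visits.

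The cost is SAP wording, settled before unblinding, and a little more analysis work in routine software. No new data are needed.

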Based on previous studies as well as data from the CRT population at Aarhus University Hospital, Skejby (n=1600) it is assumed that 35% of the population will reach the primary endpoint "death or non-planned hospitalisation for heart failure" within a period of 4 years. Based also on the above mentioned randomised controlled trial of 182 patients and up to 3 years of follow-up, and on the result of the DANISH study, this seems realistic (15). Half of these endpoints are expected to be deaths and the other half of non-planned hospitalisation for heart failure. To show a relative reduction of 25% in the incidence of this endpoint (to an absolute 26%) with $\alpha=0.05$ and $1-\beta=0.80$, n=432 patients must be included in each group. Given these

assumptions, 264 primary endpoints will occur during the study period. Assuming that no more than 10% of the patients withdraw during the study period, it will be sufficient to **include n=500 patients in each group**. Thus, a total of n=1000 patients need to be included in the study. The study is not designed to detect a significant reduction in mortality.

If, alternatively, one wanted to show a 20% reduction (from 35% to 28%), 719 patients should be included in each group (453 primary endpoints), 1500 patients in total. If one wanted to show a 30% reduction (from 35% to 24.5%) 315 patients should be included in each group, 700 in total.

Data analysis:

The primary analysis is carried out as an intention-to-treat analysis (patients randomised to the intervention group are compared with patients randomised to the control group without regard for their actual treatment). The primary data analysis will present time to the primary endpoint in Kaplan-Meier curves for each treatment group and if relevant stratification variable. Hazard ratio for reaching the primary endpoint in the intervention group relative to the control group is calculated by use of Cox regression model. Supplementary, restricted mean survival time is calculated.

Besides a non-adjusted analysis, also an analysis adjusted for age, gender, QRS morphology (LBBB/non-LBBB/RV paced), QRS width (≥ 150 ms / < 150 ms), NYHA class (II/III or outpatient IV), underlying disease (IHD/non-IHD determined heart failure), as well as including centre is done.

Subgroup analyses of the primary endpoint are planned for patients

- with different gender
- with higher and lower age (around the median)

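### A single unqualified p<0.05 rule covers all unranked secondary endpoints and 13 to 15 subgroup interaction tests, so secondary and subgroup claims of significance have no control over chance findings

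*Combined protocol and SAP*

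**What the plan says.** The Endpoints section of the Combined protocol and SAP names one primary endpoint, death or non-planned hospitalisation for heart failure. It then lists 15 secondary bullets without ranking them. Several bullets hold more than one comparison, for example "ICD therapy (time to first and number of appropriate and inappropriate ICD therapy, respectively, in addition as ATP and shock therapy, respectively".

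Under Data analysis, the primary comparison is an intention-to-treat Cox model. The section then continues in this order:

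- Subgroups: "Subgroup analyses of the primary endpoint are planned for patients", followed by the list of factors.
- Interactions: "Analysis for statistical interaction is done with respect to the subgroup-analysis above and presented graphically in a Forest plot".
- Secondary endpoints: "Secondary endpoints are compared in a similar way using Cox regression or multipel linear or logistical regression analysis". ANOVA is named for repeated measures.
- Decision rule, as the last sentence: "A p-value <0.05 is considered significant in two-sided test".

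Neither this section nor the amendment list in the Protocol document ranks the secondary endpoints, makes them conditional on the primary, divides alpha, or calls secondary or subgroup results exploratory.

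**The concern.** The rule comes directly after the interaction tests and secondary endpoints and carries no restriction. A reader following the plan would call any of those results significant at a nominal two-sided 5%. With dozens of tests, one or more such results can be expected by chance.

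The difficult case is a neutral primary endpoint beside a nominally significant secondary or interaction. The Background section describes that kind of split in the group's own earlier trial of 182 patients: clinical response was 74% versus 58% (p=0.02), with no difference in heart-failure hospitalisation or death. That trial defined response differently, since its definition also required survival without heart-failure admission. In the present trial a response based on NYHA class or walking distance is a secondary endpoint at two visits, and the plan does not say how a split result would be labelled. Background also notes that some physicians already search for late activation, so a chance finding could be taken up readily.

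**Working it through.** **1. What the 0.05 was sized for.** The Sample size section states that "it is assumed that 35% of the population will reach the primary endpoint" within 4 years, falling to 26%, with alpha 0.05 and power 0.80. For two proportions, with p̄ = 0.305 and d = 0.09:

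n = [1.96·√(2·0.305·0.695) + 0.842·√(0.35·0.65 + 0.26·0.74)]² / 0.09² = 409.6

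With continuity correction: (409.6/4)·[1 + √(1 + 4/(409.6·0.09))]² = 431.6, which rounds up to the stated 432 per group. Events: 432 × (0.35 + 0.26) = 263.5, the stated 264. The stated size therefore corresponds to one two-sided test at 0.05 on the primary endpoint. No other test enters the sizing.

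**2. Counting the tests.** The documents give no total. The counts below are read from the Endpoints, Follow-up, Patient-reported outcomes and Data analysis sections. The 12-month questionnaires are left out because the 2018 amendment omits them.

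| Secondary item | Split by visit and component | Visits merged |
|---|---|---|
| Sudden death, cardiac death | 2 | 2 |
| Clinical response, 6 and 24 months | 2 | 2 |
| 6MWT | 2 | 1 |
| NYHA class | 2 | 1 |
| KCCQ-12, PHQ-9, GAD-7 at 6, 24, 48 months | 9 | 3 |
| LVESV, LVEDV, LVEF at 6 and 24 months | 6 | 3 |
| ICD therapy | 8 | 4 |
| VT/VF | 1 | 1 |
| Atrial fibrillation (persistent; recently diagnosed) | 2 | 2 |
| Procedure time, fluoroscopy time, dose | 3 | 3 |
| LV leads used | 1 | 1 |
| Complications | 1 | 1 |
| Battery longevity | 2 | 2 |
| **Total** | **41** | **26** |

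Testing the seven listed complications separately adds 6, giving 47. Restoring the three 12-month questionnaires of Version 1 gives 50. The 2018 amendment also adds an unstated number of questionnaires at 6, 24 and 48 months.

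Subgroup interactions: gender, age, QLV, NYHA, LVEF, aetiology, LBBB, upgrade, RV septal, RV apical, dyssynchrony, scar amount and scar location make 13. There are 15 if the three dyssynchrony methods are tested separately.

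**3. Chance of at least one false positive.** Assume every null hypothesis is true and each test is two-sided at 0.05. For k independent tests the chance is 1 − 0.95^k; for k = 13, 1 − 0.95^13 = 0.487. For test statistics with common correlation ρ:

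F(k,ρ) = 1 − ∫ φ(z)·[Φ((1.96 − √ρ·z)/√(1−ρ)) − Φ((−1.96 − √ρ·z)/√(1−ρ))]^k dz

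For two families, each correlated within itself but independent of the other, the chance is 1 − (1 − F₁)(1 − F₂). The documents give no correlations, so the values 0, 0.5 and 0.8 are assumptions. Results are by numerical integration; simulation agrees to within about one percentage point.

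| Tests | ρ = 0 | ρ = 0.5 | ρ = 0.8 |
|---|---|---|---|
| 13 interactions | 49% | 33% | 19% |
| 15 interactions, or one test per secondary bullet | 54% | 36% | 20% |
| 26 secondaries | 74% | 48% | 24% |
| 41 secondaries | 88% | 58% | 28% |
| 26 secondaries + 13 interactions | 86% | 65% | 39% |

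Example for the last row at ρ = 0.5: 1 − (1 − 0.475)(1 − 0.334) = 0.650. The expected number of false positives there is 39 × 0.05 = 1.95, whatever the correlation.

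**4. Removing outcomes expected to differ.** The ethics section expects mapping to prolong the procedure, so procedure time, fluoroscopy time, dose and leads used may not be true nulls. Dropping these four leaves 22 + 13 tests: 83%, 63% and 38%.

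**The case against.** The strongest reply is that the plan already points to a single confirmatory test. It labels endpoints primary and secondary, sizes the trial on the composite alone, and says the study is not designed to show a mortality reduction. The subgroups are prespecified, confined to the primary endpoint and assessed by interaction. Many statisticians would read the rest as exploratory by convention. That describes a sensible intention, but the text does not state it, and its only rule calls any p<0.05 significant.

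Several further objections stand, and they limit the point:

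- A reader might take 41 as the number of secondary tests. The plan names ANOVA for repeated measures, which could merge visits. With 26 tests at a correlation of 0.5 the chance is 48%, just under even odds.
- A reader might infer that a false subgroup finding is more likely than not. For interactions alone that holds only for 15 near-independent tests; at a correlation of 0.5 the figure is 33% to 36%.
- A reader might infer that a stated 5% overall error rate is broken. The documents state a per-test level and promise no family-wise rate.
- A reader might infer that a secondary or subgroup result could make the trial positive and change practice. The ethics section ties practice change to confirmation of the study hypothesis, which is the primary composite.
- The LBBB contrast is a poor example of a chance subgroup, because conduction pattern is a stratification factor with a stated rationale.
- Fifteen of the 41 tests (9 questionnaire, 6 echocardiographic) concern topics referred to a PRO appendix and an imaging supplement that were not available. A hierarchy there cannot be ruled out.

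**Conclusion.** The point holds for secondary and subgroup claims only. As written, the rule labels any of about 26 to 50 secondary tests and 13 to 15 interaction tests significant at nominal 5%, with no order, gate or exploratory label in the available documents. If all nulls are true, the chance of at least one false claim across 26 secondaries and 13 interactions is about 86%, 65% and 39% at correlations of 0, 0.5 and 0.8. The lowest figure in any scenario examined is 19%, for 13 interactions at 0.8. The exact size depends on assumed correlations and on how the endpoints are counted, but the inflation persists across that range.

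The documents do not support reading this as a flaw in the primary analysis. One primary test at two-sided 0.05 keeps its error rate and power however many secondary tests follow it.

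**What to change.** Before any unblinded analysis, replace the last sentence of Data analysis with text along these lines:

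> The two-sided 0.05 significance rule applies only to the primary analysis of death or non-planned heart-failure hospitalisation. Secondary endpoints are exploratory and are reported as effect estimates with 95% confidence intervals. Subgroup interaction tests are hypothesis-generating, and the number tested is stated beside the Forest plot. Complication and device-safety outcomes are reported descriptively, without adjustment.

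If the steering committee wants a confirmatory secondary claim, it should name a short ordered list and test it in fixed sequence at 0.05, only if the primary is significant. Endpoints outside that list stay exploratory. The PRO appendix and imaging supplement should be checked for consistency with the new wording.

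The cost is a few sentences: no extra patients, data or procedures, and no effect on primary power. The downside is that secondary and subgroup results with p<0.05 outside any fixed sequence can no longer be called significant.
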